This includes genes that had been previously observed to respond to glucocorticoids (e.g., decreased expression of the cytokines IL1B and TNF), as well as genes that were previously not known to be affected by glucocorticoids (e.g., increased expression of KLF2, a transcription factor involved in T cell quiescence, regulation of T cell migration(6), negative regulation of B cell clonal expansion (7), and regulation of acute and chronic inflammation (8)). In addition, the genome-wide view of the transcriptional response provided by RNA sequencing has given us a more complete picture of the effects of glucocorticoids on hematopoietic and non-hematopoietic cell types than was previously available. Among genes that are differentially expressed in hematopoietic but not in non-hematopoietic cells after a glucocorticoid stimulus, we have observed a strong representation of TNF signaling molecules (decreased expression of TNFSF11, TNFSF14, TNF, LTA, and LTB), TLR signaling molecules (decreased expression of TLR1, TLR6, CCL3, CD80, and CCL4), and genes known to be involved in leukocyte migration and margination (CXCR4, CXCR5, KLF2).

Importantly, a number of genes known to be involved in immune function and differentially expressed in lypmhoblastoid cells are not expressed at all in fibroblasts (Figure 3), providing support for the hypothesis that there are potential targets for mimicking the immunologic effects of glucocorticoids without direct adverse consequences on non-immune cells.

**Figure 3.** Many of the immune genes that are differentially expressed in lymphoblasts at 2 and 6 hours are not expressed at all in fibroblasts. Expression levels are displayed in fragments per kilobase of transcript per million mapped reads (FPKM) in an RNA sequencing experiment 2 hours after stimulation with 1  $\mu$ M dexamethasone. The 3 columns on the left are technical triplicates of a fibroblast culture, and the 3 columns on the right are technical triplicates of a lymphoblast culture.

Finally, our in vitro data suggests that there is a significant and differential response of the noncoding genome to the glucocorticoid stimulus: Approximately 16% of the transcripts that are differentially expressed in lymphoblasts but not in fibroblasts after a glucocorticoid stimulus correspond to long-non-coding RNAs (Table 1).

	2 hours	6 hours
Total transcripts DE in lymphoblasts but not in fibroblasts	586	2047
IncRNA transcripts DE in lymphoblasts but not in fibroblasts	96	315

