# 14 Statistical Considerations

# **Definition of the Study Endpoints**

- The primary endpoint of this study is a set of lists of human genes and non-coding RNAs (small RNAs and lncRNAs) that are differentially expressed in vivo after a glucocorticoid stimulus in each of six immune cell types (B cells, CD4+ T cells CD8+ T cells, NK cells, neutrophils, and monocytes) and one non-immune tissue (skin).
- The secondary endpoint is a list of the genes and molecular pathways that represent the best candidates for targeted therapeutic alternatives to glucocorticoids.

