# **Differential Expression Analysis:**

Differential expression analysis for the RNA-seq data will be performed with the software program Cuffdiff (25). In short, the Cuffdiff algorithm models how variability in the measured fragment counts for a transcript depends on its expression level as well as its splicing structure. The algorithm captures uncertainty in a transcript's fragment count as a beta distribution and the overdispersion in this count (determined by globally fitting the observed variance in fragment counts as a function of the mean across replicates) with a negative binomial distribution. Under the resulting beta negative binomial model of fragment count variability, it estimates count variances for each transcript in each sample. These variance estimates are used for statistical testing to report significantly differentially expressed genes and transcripts. Raw p-values and False Discover Rate (FDR)-based q-values (30) are reported.

Differential expression analysis for the small-RNA-seq data will be performed in R, with the package DESeq (31). In short, the DESeq algorithm models fragment count data with a negative binomial distribution and a shrinkage estimator for the distribution's variance. Our choice of this algorithm for the small-RNA-seq data is based on the fact that most human small RNA molecules are not spliced, and DESeq uses raw fragment counts, without the assumption of spliced transcripts employed by the Cufflinks/Cuffdiff algorithms.

For each cell type, we will assess the level of variation in the baseline measurements by comparing the expression values on the day of the screening visit to the 0-hour (pre-infusion) values on the day of the glucocorticoid infusion. We will then perform differential analysis comparing each of the two post-infusion time points (2 hours and 4 hours), independently, against the baseline. We will employ a cutoff value of < 5% FDR to select the transcripts that will be considered differentially expressed in each cell type at each time point. The resulting gene lists will be contrasted to determine, for example, which genes are uniquely differentially expressed in a specific cell type, or common to a specific hematopoietic lineage (myeloid or

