lymphoid). They will also be used for pathway enrichment analysis, to determine the molecular pathways and biological functions that are most responsive to the glucocorticoid stimulus in each cell type. The genes and pathways that are found to be modified by the glucocorticoid stimulus in immune cells but not in non-immune cells (skin cells from this in vivo study and the primary human cells we have studied in vitro), will be selected as the top candidates for targeted therapeutic intervention, which we expect will form the basis of future studies.

Sequencing library preparation and sequencing batches will be carefully designed such that samples from the same subject and cell type are run in the same batch and samples from different subjects are evenly distributed across batches. This will keep batch effects to a minimum in the identification of differentially expressed genes. For analyses across different subjects, such as comparisons among different cell types, linear regression will be adopted with batch as regression variable to adjust for batch difference. While prior experience suggests that library preparation is the greatest source of batch-to-batch variation in RNA-seq experiments, if the source of batch effects is unclear or cannot be adequately modeled, the R package SVA will be used.

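### Absence of list enrichment in skin does not show that a pathway is unmodified there, so it cannot support the immune-only pathway selection

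*Combined protocol and SAP*

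**What the plan says.** All of this is in the combined protocol and SAP, Section 14.

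- **Gene lists.** Lists are built per cell type and time point: "We will employ a cutoff value of < 5% FDR to select the transcripts that will be considered differentially expressed". No fold-change cutoff is stated.
- **Pathways.** The same lists feed the pathway step: "They will also be used for pathway enrichment analysis, to determine the molecular pathways and biological functions that are most responsive". The enrichment test, its reference set and its cutoff are not named.
- **Selection.** "The genes and pathways that are found to be modified by the glucocorticoid stimulus in immune cells but not in non-immune cells" are the ones that "will be selected as the top candidates for targeted therapeutic intervention". The non-immune comparators are "skin cells from this in vivo study and the primary human cells we have studied in vitro".
- **Endpoint.** The result feeds the secondary endpoint, "a list of the genes and molecular pathways that represent the best candidates for targeted therapeutic alternatives to glucocorticoids".

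Enrichment is the only pathway-level analysis in the document. Nowhere does it say when a pathway counts as modified or not modified, and it does not ask for a check of a candidate pathway's individual genes in skin.

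**The concern.** Enrichment of a thresholded list has a relative null hypothesis: the pathway's genes are on the list no more often than other genes tested in that tissue. The selection rule needs an absolute statement about skin, namely that the glucocorticoid does not change this pathway there. The two part company when skin responds broadly. If a fifth of all skin genes respond, and a fifth of a pathway's genes among them, enrichment is correctly null although the pathway is changed.

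This differs from low power. More volunteers, or perfect detection of every gene, would not turn non-enrichment into evidence of no change.

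The secondary objective in Section 2 seeks targets that keep the therapeutic action and avoid harm elsewhere. The error runs against that aim: the wider the skin response, the more easily a pathway passes as immune-only.

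**Working it through.** The plan gives no figure for the pathway step, so there is nothing to reproduce. The check uses the standard over-representation test for a thresholded list.

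**Inputs**

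- *G*, genes tested: not given; 12,000 to 20,000 assumed.
- *m*, pathway size: not given; 50 assumed.
- *D*, skin list length: not given. Three scales are used:
  - 400–600, from the hydrocortisone microarray study in PBMCs cited under Sample Size Justification (over 400 and over 600 genes);
  - 586 and 2,047, from Table 1 in Section 1.1, row "Total transcripts DE in lymphoblasts but not in fibroblasts" (2 and 6 hours, in vitro, FDR 0.01);
  - 3,000 and 4,000, assumed, for a broad response.

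  None of these is a skin figure.
- *k*, pathway genes on the list.

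**Formula.** The one-sided enrichment p-value is P(X ≥ k), with X hypergeometric(G, D, m). The count expected by chance is mD/G.

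**Step 1: the same changes under different list lengths.** Take G = 15,000, m = 50 and k = 10 in every row.

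| List length D | Expected 50·D/15,000 | Enrichment p |
|---|---|---|
| 586 | 1.95 | 1.9 × 10⁻⁵ |
| 2,047 | 6.8 | 0.14 |
| 3,000 | 10.0 | 0.56 |
| 4,000 | 13.3 | 0.89 |

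Ten changed genes of 50 are enriched in a cell type with a short list and not enriched in a tissue with a long one. Only the list length differs.

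**Step 2: are those ten skin genes real?** At 5% FDR, about 0.05 × 10 = 0.5 of them would be expected to be false. As a rough absolute test, use the binomial tail P(at least 10 of 50) with per-gene threshold 0.05·D/G, treating genes as independent.

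- D = 2,047: threshold 0.05 × 2,047/15,000 = 0.0068, tail about 2 × 10⁻¹².
- D = 4,000: threshold 0.0133, tail about 1 × 10⁻⁹.

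The pathway is changed in skin although it is not enriched there.

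**Step 3: how many changed genes can escape?** The table gives the largest k with p ≥ 0.05 for m = 50.

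| Skin list D | G = 20,000 | G = 12,000 |
|---|---|---|
| 400 | 3 | 4 |
| 600 | 4 | 5 |
| 2,047 | 9 | 13 |
| 4,000 | 15 | 22 |

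A stricter pathway cutoff lets more through: at p < 0.001, the 2,047 row becomes 13 to 17 genes. At the other end, with G = 15,000 and a skin list of 50 to 100 genes, two changed genes already give p < 0.05. The problem is then small, and low power in skin becomes the main worry.

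**The case against.** **The rule is inferred.** The plan never equates modified with enriched. A reader might infer that it states this; it does not. What it does is offer no other pathway method and leave the word undefined. Another order of work is possible. Section 1.1 describes taking genes that respond in hematopoietic but not in non-hematopoietic cells and then finding TNF and TLR signaling well represented among them. If genes are filtered first, the ten shared genes in Step 1 drop out before any pathway is examined. This objection stands in part: the selected genes would be absent from the skin list, but the pathway named from them could still contain other genes that are on it. Section 14 does not commit to that order.

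**The size could be read as larger than it is.** In a simulation of an 80-gene pathway among 12,000 genes, with 30% of its genes responding in immune cells against 10% overall, and an equal share inside and outside the pathway in skin, enrichment was found 98.5% of the time in immune cells and 2% to 4.5% in skin. That gives 0.985 × 0.955 = 0.94 to 0.985 × 0.98 = 0.97 for an immune-only call. A reader might infer that most immune-only pathways would be wrong. The documents do not support that. This is one constructed pathway under an assumed broad skin response, the skin rate is simply the test's own error level, and the in vitro comparator is left out. Direct topical application makes a broad response plausible, but no skin list length is given. With a list of 400–600, even an 80-gene pathway escapes with at most 4–7 changed genes.

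**Downstream checks exist.** Gene-level skin lists will be available, in vitro non-immune cells are a second filter, and functional validation is a secondary endpoint in Section 2. These could expose an error. The first is not required at pathway level, and the second shares the weakness if it too relies on enrichment.

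**An absolute skin test can be too strict.** In simulation with 20 subjects and 80 genes, a subject-level sign-flip test was positive about 60% of the time with one changed gene and 88% with two. As an automatic veto it would remove pathways over one or two genes. This objection stands, and the fix reflects it.

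**Conclusion.** The point holds on the most natural reading, that a pathway is modified when it is enriched. On that reading, non-enrichment in skin cannot support the immune-only label: a 50-gene pathway can carry 3–5, 9–13 or 15–22 changed skin genes and still pass, for skin lists of 400–600, 2,047 or 4,000. These counts rest on an assumed 12,000–20,000 tested genes, a 0.05 pathway cutoff and list lengths borrowed from other settings or assumed. They show what the rule permits, not how often it would err.

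If another definition is intended, the defect shrinks to a missing definition, which still has to be written. The primary endpoint, the gene lists for six immune cell types and "one non-immune tissue (skin", is untouched. The change should be made, but it concerns the secondary endpoint only.

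**What to change.** Amend Section 14 as follows.

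1. Keep enrichment only to rank pathways within a cell type, with the transcripts tested in that cell type as the reference set. Name the test and cutoff.
2. State that non-enrichment in skin is not evidence that a pathway is unmodified.
3. Base pathway selection on a gene-set test of the immune-minus-skin difference in post-minus-pre change, in subjects who have both samples.
4. Beside each candidate pathway, list the number and identity of its genes on the skin and in vitro non-immune 5% FDR lists. Label it preferentially, not exclusively, immune when any are present.
5. Optionally report a self-contained skin test (one that asks only whether the pathway changes in skin) as supportive, not as a veto.

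**Cost.** No new samples are needed. Item 3 is a modest subject-level analysis outside Cuffdiff. Biopsies are optional and the second one is taken at 4 hours, so a time-matched contrast is limited to subjects with biopsies and 4-hour blood. Fewer pathways will be labelled immune-only.

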Blood samples will be processed for isolation of hematopoietic cell sub-populations (e.g. neutrophils, B cells, CD4+ T cells, CD8+ T cells, monocytes, and natural killer [NK] cells). Laboratory studies will be performed in the purified cells, with the goal of understanding the human response to glucocorticoids in vivo at the level of RNA (e.g., RNA sequencing, small-RNA-sequencing, real-time PCR), DNA (e.g., ChIP-seq, methylation analysis, DNA sequencing, genotyping), and protein (e.g., flow cytometry, mass spectrometry). At each time point, serum methylprednisolone levels will be measured and flow cytometry for standard lineage markers will be performed. Skin biopsies will be subjected to RNA isolation for RNA sequencing and small-RNA sequencing. A fragment of each skin biopsy will undergo fibroblast isolation and culture for in vitro exposure to glucocorticoids and for the generation of induced pluripotent stem (iPS) cells.

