#### 1.3 Choice of a Glucocorticoid and Routes of Administration

Chemical modifications to the 21-carbon corticosteroid backbone (e.g. introduction of a carbon 1-2 double bond, methylation at carbon 6, fluorination at carbon 9), have led to the diverse set of glucocorticoids that is currently available for clinical use. These modifications have mostly altered the pharmacokinetic properties of the drugs, and the relative proportion of mineralocorticoid and glucocorticoid activity, but they do not appear to have significantly altered the mechanism of action or the side effect profile of glucocorticoids. Therefore, the choice of a specific glucocorticoid for our study was based on the frequency of its use in clinical practice, the availability of reports of safe use in studies of healthy human volunteers, and the availability of an intravenous formulation (to reduce potential inter-individual variation in rates of absorption). Methylprednisolone is widely used in clinical practice, with indications in the management of diverse conditions including dermatomyositis (13), lupus nephritis (14), acute asthma exacerbations (15), and relapses of multiple sclerosis (16). Intravenous methylprednisolone has been used in multiple studies of healthy volunteers since the early 1970s (17-19), without reports of serious adverse events (SAEs) in those studies. Sodium succinate and phosphate esters are available for intravenous use. Therefore, we have identified methylprednisolone sodium succinate as the glucocorticoid of choice for our study. Because our study involves a comparison of the effect of glucocorticoids in immune and non-immune cells, in addition to blood we will serially sample a non-hematopoietic tissue. Skin is composed mostly of non-hematopoietic cells and is easily accessible, so we have selected the skin as a nonhematopoietic tissue for sampling. It is unclear from existing literature whether the concentrations of methylprednisolone in skin after intravenous administration are sufficient to induce gene expression changes after short-term administration. However, high concentrations of methylprednisolone in the skin can be achieved with topical administration. Although topical methylprednisolone is widely used in clinical practice around the world, an IND application will be required for topical methylprednisolone use in our study given that topical methylprednisolone is not currently marketed in the United States.

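### Unsorted skin RNA serves as the non-immune filter, so a gene expressed only in leukocytes may lose top-candidate status because leukocytes in the skin respond

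*Combined protocol and SAP*

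**What the plan says.** Section 14 (Definition of the Study Endpoints) defines the primary endpoint as separate lists of responding genes for six immune cell types and for skin, which it labels non-immune. The secondary endpoint is the list of best therapeutic candidates.

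Section 14 (Differential Expression Analysis) selects those candidates as "The genes and pathways that are found to be modified by the glucocorticoid stimulus in immune cells but not in non-immune cells". It names two non-immune sources: "skin cells from this in vivo study and the primary human cells we have studied in vitro". It does not say whether a change in either source disqualifies a gene or whether both must change. On the threshold it says "We will employ a cutoff value of < 5% FDR to select the transcripts"; no minimum fold change or expression level is added.

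The two arms of the comparison are prepared differently. Table 2 and the Précis describe isolation of cell sub-types for blood only. For skin, the Précis says "Skin biopsies will be subjected to RNA isolation for RNA sequencing and small-RNA sequencing", and no sorting, leukocyte depletion or adjustment for cell composition is described. The SVA package is reserved for batch effects. Section 1.3 justifies the tissue with "Skin is composed mostly of non-hematopoietic cells and is easily accessible".

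The Figure 3 caption in Section 1.1 reports "Many of the immune genes that are differentially expressed in lymphoblasts at 2 and 6 hours are not expressed at all in fibroblasts", and the text there treats this as support for the hypothesis.

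**The concern.** The natural expectation is that a few leukocytes in a skin biopsy are diluted by everything else and do no harm. That is right for a gene that all skin cells express. It is wrong for a gene that only leukocytes express. All of that gene's skin reads come from leukocytes, so its fold change in whole skin is the leukocyte fold change. Skin leukocytes are exposed to both the infusion and the topical application (Section 3), so a response is plausible.

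If such a gene is called changed in skin, the rule treats it as responding in non-immune tissue and takes it off the top-candidate list. The genes most exposed are the immune-restricted ones that Section 1.1 presents as the promising class. Nothing in the planned output would flag the reason for the loss.

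**Working it through.** **Plan's own figure.** There is none on this point. Section 14 declines standard sample-size methods and gives no effect size, variance or leukocyte share for skin.

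**Inputs from the documents.** The candidate rule and the 5% FDR cutoff (Section 14); skin mostly non-hematopoietic (Section 1.3); some responsive immune genes silent in fibroblasts (Section 1.1); initial cohort 20, maximum 50 (Sections 3 and 14); biopsies optional (Sections 3 and 6.2).

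**Assumptions, not in the documents.** Leukocyte share of skin RNA s = 1–10%; leukocyte fold change F of 2-fold or 4-fold; negative-binomial dispersion φ = 0.1–0.3; L = 100 or 1000 reads for the gene in a pure leukocyte sample; per-gene p < 0.0025 as a stand-in for 5% FDR; 10 or 20 biopsy pairs.

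**Step 1: fold change in whole skin.** Let r be expression in non-immune skin cells relative to leukocytes, and s0 and s1 the leukocyte share before and after:

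ratio = [s1·F + (1 − s1)·r] / [s0 + (1 − s0)·r]

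If r = 0 and s0 = s1, the share cancels and the ratio is F. For a 4-fold fall (F = 0.25) with r = 0.01 and s = 2%:

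(0.02×0.25 + 0.98×0.01) / (0.02 + 0.98×0.01) = 0.0148 / 0.0298 = 0.497, log2 = −1.01

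| r | s = 2% | s = 5% | s = 10% |
|---|---|---|---|
| 0 | −2.00 | −2.00 | −2.00 |
| 0.01 | −1.01 | −1.44 | −1.68 |
| 1 | −0.02 | −0.06 | −0.11 |

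Entries are whole-skin log2 fold changes. The effect falls on immune-restricted genes and nearly vanishes for genes expressed equally everywhere.

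**Step 2: probability of being called changed in skin.** Selection is on FDR, so the fold change alone does not decide. With m0 = s·L and m1 = m0·F, an unpaired Wald test on the log ratio has

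V = [(1/m0 + φ) + (1/m1 + φ)] / n, probability ≈ Φ(|ln F|/√V − 3.02)

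Example: 2-fold fall, L = 100, s = 2%, n = 10, φ = 0.1. Then m0 = 2, m1 = 1, V = (0.6 + 1.1)/10 = 0.17, |ln F|/√V = 0.693/0.412 = 1.68, and the probability is Φ(−1.34) = 0.09.

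| Leukocyte change | Pairs | s | L | φ = 0.1 | φ = 0.3 |
|---|---|---|---|---|---|
| 2-fold fall | 10 | 2% | 100 | 0.09 | 0.07 |
| 2-fold fall | 10 | 2% | 1000 | 0.75 | 0.31 |
| 4-fold fall | 10 | 2% | 100 | 0.36 | 0.30 |
| 4-fold fall | 10 | 2% | 1000 | 1.00 | 0.96 |
| 2-fold rise | 20 | 1% | 100 | 0.26 | 0.19 |
| 2-fold rise | 20 | 5% | 100 | 0.91 | 0.60 |
| 2-fold rise | 20 | 5% | 1000 | 1.00 | 0.81 |

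Monte Carlo (20,000 runs, t-test on log counts) gave 0.998 and 0.64 for the last row, and 0.14 for the fifth row at φ = 0.3. The Wald values are therefore somewhat optimistic at the higher dispersion. At p < 0.0005 the last row becomes 1.00 and 0.66.

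**Step 3: unstable leukocyte share.** With r = 0 the ratio is F·(s1/s0). If the share halves, a non-responding gene (F = 1) shows 0.5, which mimics a fall, and a doubled gene (F = 2) shows 1.0, which masks the rise. If the share grows by half, F = 2 shows 3.0. Section 11.2 expects shifts in blood leukocyte counts after dosing; the documents do not say what happens in skin.

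**The case against.** The strongest reply is that an undiluted ratio is not the same as removal. Low counts mean low power, biopsies are optional, and the second biopsy is at 4 hours while some volunteers follow the 1- and 2-hour blood regimen (Section 3), so pairs may be well below 20. This stands. A reader might infer that every leukocyte-only gene is removed; the table in the working shows that is not so.

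Second, a reader might infer that any movement of leukocytes out of skin has the same effect. It does not: exit mimics or strengthens a fall, but hides a rise, and Section 1.1 describes genes moving in both directions.

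Third, Section 14 does not rely on skin alone, and it does not say that a change in skin by itself disqualifies. If both sources had to change, a leukocyte-only gene would survive. The either-source reading is the more natural one, but it is an inference, and the plan should settle it.

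Fourth, the gene is not lost from the study. It stays on every immune cell-type list, and marker transcripts in the same skin data could reveal a leukocyte contribution later. This also stands, and limits the harm to the candidate step.

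Finally, exclusion criterion 6 bars skin conditions that could affect skin transcription, which removes some inflamed skin. It does not make the remaining skin free of leukocytes.

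**Conclusion.** The concern holds in a conditional form. As written, the rule may strip top-candidate status from immune-restricted genes because the leukocytes inside the non-immune comparator respond. This is likely for abundant, strongly responding genes (96–100% for a 4-fold fall, 1000 leukocyte reads, 2% share, 10 pairs) and unlikely for low-count genes with few pairs (7–9% for a 2-fold fall, 100 reads, same share and pairs).

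The equality of fold changes needs only two conditions: no expression in non-immune skin cells and a stable leukocyte share. The detection probabilities rest on assumed share, dispersion, read count and p cutoff. Removal also requires that skin leukocytes respond to the drug and that a change in either source disqualifies.

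A reader might infer that the primary endpoint is compromised. As Section 14 defines it, the primary endpoint is a set of lists per cell type or tissue, and those lists are unaffected. The affected output is the secondary-endpoint candidate list. The change should be made because it is cheap and must be set before the lists are seen; the point does not undermine the trial.

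**What to change.** In Section 14 (Differential Expression Analysis):

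1. State that a change in either non-immune source counts against a gene, with one exception. A change in skin alone removes a gene from the top candidates only if the gene is expressed, above a threshold fixed before the lists are seen, in the laboratory's existing in vitro non-immune RNA-seq data.
2. Put genes that change in skin but fall below that threshold in a separate tier, labelled as *skin change possibly from resident leukocytes*.
3. Report leukocyte marker transcripts in the skin samples before and after drug, so that a shift in leukocyte share can be seen.

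The rule should not depend on the fibroblast lines grown from these biopsies, because Section 7 leaves their in vitro testing to the future.

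**Cost.** A few sentences in Section 14, a lookup in data already held and a summary of markers already sequenced; no new sample or visit. **Downside.** The in vitro reference is narrow: Figure 3 shows technical triplicates of one fibroblast culture. A gene expressed in keratinocytes or other skin cells but not in the cultured cells could land in the separate tier, which is why that tier is reported apart from the top candidates.

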#### FDR for differential expression: 0.01

**Table 1.** Approximately 16% of the transcripts that are differentially expressed in immune but not in non-immune cells after a glucocorticoid stimulus correspond to long non-coding RNAs. FDR=False Discovery Rate

At the completion of this study, we expect to generate a list of human genes and non-coding RNAs that are differentially expressed and regulated in response to glucocorticoids between immune and non-immune cells in vivo. These data will be used to identify transcripts, their corresponding proteins, and the molecular pathways that are best candidates for targeted intervention. Potential targets could then be validated with siRNA libraries, with the long-term goal of developing small-molecule (9, 10) or nanoparticle-facilitated-RNAi (11, 12) interventions that reproduce the therapeutic action of glucocorticoids in immune cells while avoiding the harmful side effects of this class of drugs on other tissues.

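### Section 14 selects immune-specific candidates by subtracting one significance list from another, with no test of the difference in response, so genes that respond equally in blood and skin can be listed as immune-specific

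*Combined protocol and SAP*

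**What the plan says.** Section 14, Differential Expression Analysis, compares each post-infusion time point with baseline separately within each cell type. The threshold is: "We will employ a cutoff value of < 5% FDR to select the transcripts that will be considered differentially expressed in each cell type". The comparison between cell types is then made on the lists: "The resulting gene lists will be contrasted to determine, for example, which genes are uniquely differentially expressed in a specific cell type". The top therapeutic candidates are the genes and pathways altered in "immune cells but not in non-immune cells (skin cells from this in vivo study and the primary human cells we have studied in vitro").

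The one sentence about modelling across cell types says that "linear regression will be adopted with batch as regression variable to adjust for batch difference". It names no term for response by tissue, no hypothesis and no decision rule.

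Sections 3 and 6.2 make both skin biopsies optional. Neither these sections nor the sample-size text gives a number of skin pairs.

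The endpoint definitions differ. The Protocol Summary and Section 2 define the primary endpoint as a list of differences in response between immune and non-immune cells. Section 14 makes the separate per-tissue lists primary and the candidate list secondary.

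**The concern.** The scientific question is whether a gene's response differs between tissues. The written rule asks something else: whether the gene crossed a threshold in one tissue and missed it in another. A gene can miss 5% FDR in skin because it does not respond there, or because too few skin samples were available to show that it does. The rule treats both as absence of response.

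The direction of the error is awkward. Fewer biopsies mean fewer significant genes in skin, hence fewer genes removed, so the immune-specific list can grow as the evidence weakens. Genes listed in error would be reported as immune-specific and would use validation effort, although the purpose of the list is to find targets that spare non-immune tissue.

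**Working it through.** **The documents' own figures.** Section 1.1, Table 1 applies the same kind of subtraction to the in vitro data ("Total transcripts DE in lymphoblasts but not in fibroblasts"). Its percentages reproduce: 96/586 = 16.4% and 315/2,047 = 15.4%. They describe lists already formed by subtraction and do not show how many entries are truly specific. The initial 20 subjects are justified by analogy with a PBMC pilot study. No effect size, SD or power is given, so that number cannot be recomputed, and the argument does not address skin.

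**Inputs.** From the documents: an initial cohort of 20 and optional biopsies. Assumed, because the documents give no values: the same standardised change d in both tissues, equal SD of change, independent errors, paired t tests, a fixed per-gene threshold standing in for the 5% FDR cut, one immune cell type against skin, 20 blood pairs, 20, 10 or 5 skin pairs, and no in vitro filter.

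**Step 1: chance that an equal responder is listed as immune-only.**

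P(listed) = power in blood × (1 − power in skin), with power from the noncentral t distribution on n − 1 degrees of freedom and noncentrality d√n.

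| d, threshold | Blood power (20 pairs) | Skin power (20 / 10 / 5 pairs) | Listed as immune-only (20 / 10 / 5) |
|---|---|---|---|
| 1.0 SD, p<0.001 | 0.707 | 0.707 / 0.160 / 0.017 | 21% / 59% / 70% |
| 1.5 SD, p<0.005 | 0.999 | 0.999 / 0.810 / 0.192 | 0.1% / 19% / 81% |
| 0.5 SD, p<0.001 | 0.087 | 0.087 / 0.017 / 0.004 | 8% / 9% / 9% |

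For the first row: 0.707 × (1 − 0.707) = 0.207; 0.707 × (1 − 0.160) = 0.594; 0.707 × (1 − 0.017) = 0.695.

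**Step 2: the same gene under an added difference test.** With equal changes the mean of immune change minus skin change is zero. A paired test of that difference at p<0.001 is therefore passed 0.1% of the time, whatever the number of skin pairs. Requiring it as well as the present condition caps the chance of listing at 0.1%.

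**Step 3: what the added test costs.** Take a gene that truly responds only in the immune cell. With independent errors its standardised difference is d/√2. For d = 1.0 this is 0.707, and power at p<0.001 is 29%, 5% and 0.7% with 20, 10 and 5 volunteers giving both samples. For d = 1.5 it is 1.061, and power at p<0.005 is 92%, 43% and 8%.

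**The case against.** **The regression sentence.** It shows that comparisons among cell types were not meant to rest on lists alone. That stands, but as written it adjusts for batch and is not tied to candidate selection.

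**The in vitro comparator.** A candidate must also be unmodified in the primary cells studied in vitro, which would remove some equal responders. That stands, and the share removed is unknown. The in vitro results shown use subtraction too, at a stricter cut ("FDR for differential expression: 0.01") and after dexamethasone. For Figure 3, "The 3 columns on the left are technical triplicates of a fibroblast culture". The documents do not say that these data are the whole comparator set, so a reader might infer that the filter is worthless; they do not support that.

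**Genes absent from the comparator.** Section 1.1 says that a number of immune-function genes "differentially expressed in lypmhoblastoid cells are not expressed at all in fibroblasts". These are a genuine and different group. The rule does not separate them from genes that merely missed significance.

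**The illustration is not the planned analysis.** Section 14 plans Cuffdiff and DESeq and specifies no pairing or subject term. This stands in full: the figures show that the error can occur, not how often it would occur here.

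**Exploratory purpose.** Functional validation is itself a secondary endpoint and may catch false entries. It does so only after they have been called immune-specific.

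**Conclusion.** The point holds and should be fixed before candidates are selected. Followed exactly, Section 14 can list genes that respond equally in both tissues as immune-specific, and it has no step designed to prevent this.

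The logic rests on the text alone. The size rests on assumed effects, skin numbers and paired t tests. In the illustration it runs from 0.1% (1.5 SD, 20 skin pairs) to 81% (1.5 SD, 5 skin pairs) for a single equal responder. It is negligible if effects are large and skin is fully sampled.

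Two stronger readings are not supported. A reader might infer that 59% or 70% of the candidate list would be false. Those figures are the chance for one gene assumed to respond equally; the share of the list depends on a mix of genes that the documents do not give. A reader might also infer that the primary endpoint is invalid. Section 14 makes the per-tissue lists primary, and 5% FDR per list suits them. Which list is primary is a separate inconsistency and does not raise the weight of this point.

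**What to change.** In Section 14:

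- **Keep the present condition**: significant in the immune cell type, not significant in the non-immune comparators. A difference test alone would admit genes clearly significant in skin whenever the immune change was larger.
- **Add a test before calling a gene immune-specific**: immune change minus skin change at 4 hours within subject (tissue-by-time contrast, subject as blocking factor), at FDR <5%, with the larger change in the immune cell type. State the set of genes over which this FDR is computed.
- **Use the same kind of contrast** for genes described as unique to one cell type.
- **Report for each candidate** the skin estimate, its confidence interval and the number of skin pairs.
- **Label the rest.** Genes that pass the present condition but not the contrast stay on the list as *immune response detected, skin response not established*. Genes absent from the comparator are labelled *not expressed in comparator*. Neither group should be called *not modified*.
- **State the exposure difference.** Skin receives topical as well as intravenous drug, so a difference may partly reflect exposure.

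Separately, reconcile Section 14 with the Protocol Summary and Section 2 on which list is the primary endpoint.

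**Cost.** SAP wording and analysis time, with no extra samples. Only volunteers with both 4-hour blood and a biopsy contribute; those on the 1- and 2-hour regimen have no 4-hour blood. The confirmed list will be shorter and may be nearly empty with about 10 or fewer skin pairs. The labels keep the remaining genes visible.
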